1.10 Timetable/Schedule of Events

| | 2018 | 2019 | 2020 | 2021 | 2022 |
|---|------|------|------|------|------|
| Rutgers / UBHC project meeting | x | x | x | x | x |
| Train study therapist and research asst. | x | x | x | x | x |
| Recruit participants (N=90; 30/yr; 3/month) | x | x | x | x | |
| Complete follow up assessments | | x | x | x | x |
| Data Analysis | | | | x | x |

2.2 Resources Available

Facilities- Participants will be daily smokers from New Jersey. Participants will attend treatment remotely using an online telehealth HIPAA compatible platform. Participants will be in the state of New Jersey during any counseling sessions though they may be outside of New Jersey (e.g., if they are traveling) for follow-up research assessment appointments.

Medical Or Psychological Resources- [name] is a licensed clinical psychologist in that state of New Jersey and will assist in training study staff in the management of crisis intervention. In addition, they will be available 24/7 to field any questions/concerns study staff have regarding how to proceed in the event that participants experience unanticipated psychiatric distress during the course of the study.

Research Staff Training- All graduate students and research assistants will complete intensive training with [name], including proper administration of each intervention condition and proper administration and management of nicotine replacement therapies. All graduate students will also complete weekly supervision with [name].

3.0 Multi-Site Research Communication & Coordination

N/A

3.1 Outside Research

N/A

4.0 Research Data Source/s

4.1 Primary Data-Subjects and Specimens

Research participants will be 61 daily cigarette smokers with schizophrenia, schizoaffective disorder, or bipolar disorder. We will collect questionnaire data and expired breath carbon monoxide. We will provide 8-weeks of free counseling to participants and 10 weeks of nicotine transdermal patch (an FDA-approved, over-the-counter medication).

4.2 Subject Selection and Enrollment Considerations

A. Recruitment Details

Research assistants will post flyers at UBHC and will work with staff for help in connecting with potential participants. Research assistants will post flyers and place leaflets in local areas.

B. Source of Subjects

We will recruit smokers from Rutgers University Behavioral Health Care, from the community via our website and local flyers, via social media, via Rutgers listservs, local agencies or organizations who serve mental health consumers (i.e. CHOICES, SERV Behavioral Health Systems, Inc.; George J. Otlowski, Sr. Center for Mental Health Care, Hunterdon Behavioral Health Care), and ElevateU's Study Recruitment Platform (explained above in section 1.3 1.3 Research Design and Methods).

C. Method to Identify Potential Subjects

Participants responding to flyers or otherwise referred will complete a telephone screen to determine likely eligibility. If potentially eligible, they will be offered a more in-depth telehealth appointment screening after providing informed consent. If all inclusion criteria are met, they will be invited to participate.

D. Subject Screening

Interested participants will complete a brief telephone screening where they will be assessed by trained study personnel who will determine initial eligibility.

Inclusion Criteria

- Must be between 18 – 70 years old
- Must indicate willingness to make a quit attempt in the next 30 days
- Must report being a daily smoker (including those labeled “little cigars”) for past month
- Must have a diagnosis of Schizophrenia, Schizoaffective Disorder, or Bipolar Disorder on SCID-5-RV
- Psychiatric illness must be stable, as indicated by no hospitalizations in previous 8 weeks, and a stable psychotropic medication regimen for 8 weeks

- Must have a smartphone, tablet, or computer with ability to download apps
- Must currently receive mental health treatment
- Must sign release of information for current mental health treatment providers

Exclusion Criteria

- Must not currently (in past 10 days) be taking varenicline (Chantix),
- Must not currently (in past 10 days) be taking bupropion (Zyban/Wellbutrin) to quit smoking.
- Must not be taking any nicotine preparations (gum, lozenge, patch, spray, inhaler) daily over the last 10 days
- Must not be currently receiving tobacco dependence treatment counseling.
- Must not report myocardial infarction, unstable angina pectoris, or significant cardiac arrhythmia (including atrial fibrillation) in the past 30 days.
- Women must not be pregnant, nursing, or planning on becoming pregnant in the next three months. Women who can become pregnant may be included if using effective birth control.
- Must not have pending legal matters with potential to result in jail time
- Must not be planning on moving outside of New Jersey in next 3-months
- Problematic substance use in the past 3 months (AUDIT-C score ≥ 5 for men and ≥ 4 for women, DAST-10 score of ≥ 4)
- Must not have suicidal ideation in the past week with intent, plan, or access to method; must not have attempted suicide in the past year (as assessed on the SCID-RV)

E. Recruitment Materials

We will rely upon flyers and consumer letters. We will also give UBHC staff a handout to use for reference when making referrals. Please see attachments. We additionally anticipate recruitment of participants via word-of-mouth.

F. Lead Site Recruitment Methods

N/A

4.3 Subject Randomization

N/A

4.4 Secondary Subjects

N/A

4.5 Number of Subjects

A. Total Number of Subjects

N=120

B. Total Number of Subjects If Multicenter Study

N/A

C. Require Number of Subjects to Complete Research

N=61

D. Feasibility of Recruiting

We anticipate enrolling 3 participants monthly over the course of 3 years. Based on previous research conducted by the principal investigators this should be feasible. This is an urban area with a large low-income population and therefore a greater proportion of smokers than the average of 14.8% in the state of New Jersey. Previous studies have given us the necessary experience with Rutgers listservs, websites, Craigslist, and use of flyers and brochures to maximize recruitment.

4.6 Consent Procedures

A. Consent

- **Documenting Consent**

All participants will provide electronically signed informed consent using the HIPAA compatible survey platform, RedCap or Qualtrics after being given the opportunity to read the consent form in full and to ask questions about the research. A research assistant will also electronically sign the consent form as a witness.

- **Waiver or Alteration of Consent Process**

N/A

B. Consent Process

- **Location of Consent Process**

Verbal consent will be obtained for the initial phone screen. The PI or RA will first explain the purpose of the phone screen and limits of confidentiality and provide an overview of the study. If potential participants remain interested, they must verbally agree to phone screen completion.

During the initial telehealth meeting, study personnel will verbally go over the consent form including details regarding the procedure, time commitment, payment, risks/benefits, and option to discontinue at any time without penalty, and ask the participant questions to ensure they understand.

- **Ongoing Consent**

N/A

- **Individual Roles for Researchers Involved in Consent**

A trained research assistant (who will receive weekly and as-needed supervision from the principal investigator) will pre-screen potential participants on the phone, followed by obtaining informed consent and administering the baseline assessment battery.

1. Consent Discussion Duration

Staff will go over details regarding the procedure, time commitment, payment, risks/benefits, and option to discontinue the study at any time without penalty. We anticipate that it will take participants 5 minutes to read the consent and up to an addition 5 for staff to review relevant information.

2. Coercion or Undue Influence

Potential participants will explicitly be told in the consent form that the study is completely voluntary and that they may withdraw without penalty at any time. We will inform participants who wish to withdraw, who do not wish to participate, and who do not meet inclusion criteria about alternative cessation treatment options.

3. Subject Understanding

Participants will read a consent form or will have the consent form read to them before signing it. Trained research staff will proactively ask participants to describe the research

study to them in their own words to ensure that participants understand the consent form. If there is any doubt of competence to consent, the individual will not be enrolled. In addition to providing written informed consent, participants must verbally indicate that they understand the study procedures and that they have no further questions.

4.7 Special Consent/Populations

N/A

4.8 Economic Burden and/or Compensation for Subjects

A. Expenses

N/A

B. Compensation/Incentives

Participants will be paid \$100 through the duration of the study. They will receive \$35 at the initial assessment, \$30 at the post-counseling assessment (after session 8), and \$35 at the 3-months post-quit date assessment. Participants will be paid via the Rutgers ClinCard system.

B.1 We may divide the baseline assessment battery into two sessions to minimize participant fatigue if necessary.

C. Compensation Documentation

We will maintain a full accounting of funds using the Rutgers ClinCard system.

4.9 Risks to Subjects

A. Description of Subject Risk

There is a risk of discomfort associated with nicotine withdrawal for patients who are quitting smoking. The nicotine patch (an FDA-approved medication) is well tolerated; however, there are potential side effects that may arise when using the patch. Potential side effects include dizziness, headache, nausea, vomiting, diarrhea, or redness or swelling at the patch site. Each patient will discuss these side effects with their therapist. If questions arise as a result of the patch, one of the study co-investigators is an Addiction Psychiatrist who will be available to provide patients with information regarding their side effects.

The overall risk of AEs in this study is expected to be low because both the counseling sessions and the use of over-the-counter nicotine replacement products are low risk and similar to established treatments to help smokers quit. We will monitor patients for AEs at every session, however, and any AEs that are deemed to be moderate to severe will be reviewed by addiction psychiatrist, [name] and discussed at the weekly research meetings. The team will document the recommended actions with input from [name]. AEs will be followed until they resolve or until participant study completion. The AE Tracking Form and AE specifics log will also be completed.

There is a risk that participants' confidentiality could be violated. To reduce the risk of violating confidentiality, several steps will be taken. Only IRB approved members of the research team will have access to the data. All computers used by research staff will be password protected with complex passwords. The participants google email account will only include their participant ID number and we will ask that participants do not use this account for communication outside of the research study to protect their confidentiality. Data will only be accessed when coded, entered, or audited. The PI will maintain responsibility for safe data storage. All data will be stored in locked cabinets within locked rooms. We will use a telehealth platform that is HIPAA compatible (e.g. Microsoft Teams, Doxy.me, or zoom). Based on these procedures, we anticipate that the risk to confidentiality is very low.

B. Procedures for Risks to Embryo, Fetus, and/or Pregnant Subjects

N/A

C. Risks to Non-Subjects

N/A

D. Assessment of Social Behavior Considerations

Study risks are minimal and include a small, temporary increase in distress as a result of the assessments; however, the methodologies employed have been utilized in many labs and clinical settings with hundreds of participants suffering from a range of psychopathology, and approved by as many IRBs.

▪ Reasonably Foreseeable Risks

Study risks are minimal and include a small, temporary increase in distress as a result of the assessments. Participants who quit may experience at least mild nicotine withdrawal symptoms even with counseling and nicotine replacement therapy.

▪ Risk Of Imposing An Intervention On Subject With Existing Condition

N/A

▪ Other Foreseeable Risks

Our research team employs standard procedures to ensure confidential information about study participation is not disclosed. All data are linked to an arbitrary 3-digit study ID unrelated to personal information. The file linking participants to their study ID will be stored in a password-protected file, located within a password-protected database on an encrypted computer. Only select trained laboratory personnel will have access to the file. All computer files or printed data used for analysis also will be de-identified. Informed consent collected remotely will be stored in HIPAA compatible survey platform, RedCap. Physical consent forms and payment forms will be stored in a locked file cabinet separate from data in an office that is locked when not occupied. Participants' confidentiality also is protected by never associating a participant's name with results in any published or otherwise publicly presented report. Demographic information, including information about participants' age, ethnicity, education, marital status and employment status, will be reported using averages and percentages computed over multiple participants and never reported at the level of individual participants.

▪ Observation And Sensitive Information

N/A

E. Minimizing Risks

Participants will be instructed to call 911 if they experience a medical emergency and Acute Psychiatric Services (APS) at [contact] if they experience a psychiatric emergency. Patient will be counseled and provided with appropriate emergency contact information in the event a research assistant or study therapist determines that emergency care is warranted.

Our research team employs standard procedures to ensure confidential information about study participation is not disclosed. All data are linked to an arbitrary 3-digit study ID unrelated to personal information. The file linking participants to their study ID will be stored in a password-protected file, located within a password-protected database on an encrypted computer. Only select trained laboratory personnel

will have access to the file. All computer files or printed data used for analysis also will be de-identified. Informed consent collected remotely will be stored in HIPAA compatible survey platform, RedCap. Physical consent forms and payment forms will be stored in a locked file cabinet separate from data in an office that is locked when not occupied. Participants' confidentiality also is protected by never associating a participant's name with results in any published or otherwise publicly presented report. Demographic information, including information about participants' age, ethnicity, education, marital status and employment status, will be reported using averages and percentages computed over multiple participants and never reported at the level of individual participants.

All technology platforms handling PHI will be HIPAA compatible and our team is well trained in HIPAA compliance.

F. Certificate of Confidentiality

We have obtained a Certificate of Confidentiality from the National Institutes of Drug Abuse.

G. Potential Benefits to Subjects

The benefits of taking part in this study include access to high-quality, smoking cessation treatment based on empirically supported psychosocial approaches. If participants quit smoking, they will experience health benefits; however, they may receive no direct benefit from taking part in this study.

H. Provisions to Protect the Privacy Interests of Subjects

Our research team employs standard procedures to ensure confidential information about study participation is not disclosed. All data are linked to an arbitrary 3-digit study ID unrelated to personal information. The file linking participants to their study ID will be stored in a password-protected file, located within a password-protected database on an encrypted computer. Only select trained laboratory personnel will have access to the file. All computer files or printed data used for analysis also will be de-identified. Informed consent collected remotely will be stored in HIPAA compatible survey platform, RedCap. Physical consent forms and payment forms will be stored in a locked file cabinet separate from data in an office that is locked when not occupied. Participants' confidentiality also is protected by never associating a participant's name with results in any published or otherwise publicly presented report. Demographic information, including information about participants' age, ethnicity, education, marital status and employment status, will be reported using averages and percentages computed over multiple participants and never reported at the level of individual participants.

I. Research Team Access to Subject Data

Only IRB approved staff will have access to participant data. All data will be coded by arbitrary study number to ensure confidentiality and will be stored in a locked filing cabinet or stored on the lab server where access will be password-protected. Data collected online will be de-identified (e.g., associated with an arbitrary study ID number) and only accessible to trained study personnel. Informed consent collected remotely will be stored in HIPAA compatible survey platform, RedCap. Physical consent forms with identifying information (names) will be filed separately from actual study data in a separate locked filing cabinet. This cabinet the office in which it is kept will ensure that it is also double-locked.

4.10 Secondary Data – Records/Chart Reviews/Databases/Tissue Banks/etc.

N/A

4.11 Chart/Record Review Selection

N/A

4.12 Secondary Specimen Collection

N/A

5.0 Special Considerations

5.1 Health Insurance Portability and Accountability Act (HIPAA)

We will be obtaining and/or disclosing individually identifiable health information associated with a HIPAA-covered component or entity. See attachments for release of information and request of information forms.

Informed consent, release of information , and request for information collected remotely will be stored in HIPAA compatible survey platform, RedCap. All technology platforms handling PHI will be HIPAA compatible and our team is well trained in HIPAA compliance.

5.2 Family Educational Rights and Privacy Act (FERPA)

N/A

5.3 NJ Access to Medical Research Act

N/A

5.4 Code of Federal Regulations Title 45 Part 46 (Vulnerable Populations)

N/A

6.0 Research Data Protection and Reporting

6.1 Data Management and Confidentiality

A. Hypothesis 1: The PTSC-S intervention will be acceptable to participants, and the study will be feasible to conduct as evidenced by:

- a. At least 80% of participants will provide at least a 5 on a 1 – 7 scale regarding how “useful” the intervention was, how acceptable the length of each session was, and how acceptable the number of counseling sessions offered was (with higher scores reflecting ratings of more useful and more acceptable). Analysis 1a: Descriptive statistics will be reported.
- b. We will achieve follow-up rates of at least 80% at the 3-month follow-up. Analysis 1b: Descriptive statistics will be reported.
- c. Rates of missing/unusable data will be < 10% of all data collected. Analysis 1c: Descriptive statistics will be reported.

Hypothesis 2: As compared to baseline, participants will report greater task persistence as evidenced by reduced scores on the Thoughts About Smoking Questionnaire (TASQ). Analysis 2: One-tailed, paired sample t-tests will be used to examine decreases in scores on the TASQ at each timepoint.

Hypothesis 3: As compared to baseline, participants will report smoking fewer cigarettes per day at 1- and 3-month follow-up. Analysis 3: One-tailed, paired sample t-tests will be used to examine decreases in cigarettes smoked per day on the TASQ at each timepoint.

B. We determined the sample size based on data from the R21 phase of the study, we can expect a large effect (Cohen's $dz = 1.28$) of the intervention on task persistence as measured by the Thoughts About Smoking Questionnaire (TASQ). We detected a change in mean(SD) scores, in the predicted direction, from 4.371(1.0) at baseline to 3.218(1.1) at follow-up. An effect of $dz = 1.28$ setting power at 80% and alpha at 0.05 suggests we need $N = 6$ participants in the within-subjects analysis to detect an effect (see Figure 1 below).

Because effect sizes may be unstable at smaller sample sizes, we will be much more conservative and assume an effect size of Cohen's $dz = 0.5$ (consistent with a medium, rather than a very large effect size). Given a medium effect size, while setting power at 80% and alpha at 0.05, we will require $N = 27$ participants for this within-subjects design (see Figure 2 below). While we will impute baseline data where follow-up data are missing (i.e., assuming no improvement), we will also recruit additional participants to account for the possibility of up to 20% loss to follow-up (i.e., 80% retention rate). We will therefore aim to recruit 34 additional participants to have $N = 27$ with complete data at follow-up after making the protocol changes described within this document.

C. Data Handling: Only IRB approved members of the research team will have access to the data. The research staff collecting the data will bring the data to the PI within 24 hours of it being collected. Data will only be accessed when coded, entered, or audited. The PI will maintain responsibility for safe data storage. All data will be stored in locked cabinets within locked rooms.

Data collection: The data will be collected through telehealth video interview using HIPAA compliant platform (e.g. Microsoft Teams, Doxy.me, or zoom). If telehealth video appointments are unable to be done because of internet connectivity, we will conduct telephone interviews. Data will be stored at the Division of Addiction Psychiatry; [name]. Only the IRB-approved research team will have access to the research data.

Data entry, editing and management, including handling of data collection forms, different versions of data, and data storage and disposition: Data will only be accessed and handled by IRB approved study personnel and kept in password protected databases. [name] is ultimately responsible for the receipt and transmission of all data. Informed consent collected remotely will be stored in HIPAA compatible survey platform, RedCap. Paper copies of data (e.g., names on consent forms) will be stored immediately in Rutgers offices where they will be locked in a cabinet housed behind a locked door (of Division of Addiction Psychiatry, [name]).

All computer files will be kept on computers requiring login and complex passwords for entry, and all files with identifying information will have the extra protection of a password to open that individual file. The individual participant's personal information, including name and contact numbers, will be kept separate from their study data and linked only by a study number assigned by the PI. The master link between the study number and patient contact information will be destroyed once all data is collected and checked for accuracy. The confidential binder containing telephone screen forms will be shredded and properly discarded after 12 months of study completion. Participant names will not be used in any publications or papers derived from this study.

Additionally, we have obtained a Certificate of Confidentiality from the NIH.

- D. Qualtrics and Excel databases will be created in such a way as to not allow for out of range data.
- E. Data (described in section 1.6 B) will only be accessed and handled by IRB approved study personnel and kept in password protected databases. [name] is ultimately responsible for the receipt and transmission of all data. Paper copies of data (e.g., names on consent forms) collected at the UBHC will be brought immediately to Rutgers offices where they will be locked in a cabinet housed behind a locked door (of Division of Addiction Psychiatry, [name]).

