1.4 Preliminary Data

Our pilot study (N=26) examining the PTSC-S intervention demonstrated that we could successfully follow-up this population (20 of 26 participants were reached at end-of-treatment). In addition, we demonstrated that our intervention engaged our target mechanism (i.e., task persistence). While there was no change in persistence on multiple measures, we did find that as hypothesized, scores on the Thoughts About Smoking Questionnaire (TASQ) showed significant decreases from baseline to the target quit date, $t(16) = 7.753$, $p < 0.001$, and maintained those significant decreases from baseline to end-of-treatment, $t(19) = 4.537$, $p < 0.001$. These data indicate that our PTSC-S intervention positively influenced cognitive aspects of our target mechanism, thus meeting milestone 1. More specifically, our intervention was able to positively influence cognitions likely to dampen task persistence.

We also found that 57.7% of participants met our target of attending at least 6 of 8 sessions. Importantly, early in the study, we noticed that patients were having difficulty with transportation and therefore were missing many sessions. We therefore instituted a protocol in which we were able to provide transportation to the participants and this has increased participant attendance in treatment. When excluding the first 5 patients from the equation (those who did not have the benefit of transportation provided to them), we find that 66.7% of participants attended at least 6 of 8 of their PTSC-S treatment sessions.

Finally, participants found the intervention to be easy to understand and helpful. In response to the statement, "Overall, this treatment was easy to understand," 68.8% of participants endorsed "7: Totally Agree" with an additional 18.8% endorsing "6: Agree very much" for a total of 87.6% endorsing at least a 6 out of 7In response to

the statement, “Overall, this treatment was helpful,” 56.3% of participants endorsed “Totally Agree” with an additional 25% endorsing “Agree very much” for a total of 81.3% endorsing at least a 6 of 8.

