1.5 Sample Size Justification

Based on data from the R21 phase of the study, we can expect a large effect (Cohen’s $dz = 1.28$) of the intervention on task persistence as measured by the Thoughts About Smoking Questionnaire (TASQ). We detected a change in mean(SD) scores, in the predicted direction, from 4.371(1.0) at baseline to 3.218(1.1) at follow-up. An effect of $dz = 1.28$ setting power at 80% and alpha at 0.05 suggests we need $N = 6$ participants in the within-subjects analysis to detect an effect (see Figure 1 below).

Because effect sizes may be unstable at smaller sample sizes, we will be much more conservative and assume an effect size of Cohen’s $dz = 0.5$ (consistent with a medium, rather than a very large effect size). Given a medium effect size, while setting power at 80% and alpha at 0.05, we will require $N = 27$ participants for this within-subjects design (see Figure 2 below). While we will impute baseline data where follow-up data are missing (i.e., assuming no improvement), we will also recruit additional participants to account for the possibility of up to 20% loss to follow-up (i.e., 80% retention rate). We will therefore aim to recruit 34 additional participants to have $N = 27$ with complete data at follow-up after making the protocol changes described within this document.

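### Does Hypothesis 1a count participants who give no rating as failures, putting its 80% acceptability bar out of reach?

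*Combined protocol and SAP*

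**What the plan says.** Section 6.1 A gives three criteria for Hypothesis 1.

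- **1a, acceptability:** "At least 80% of participants will provide at least a 5 on a 1 – 7 scale". This covers usefulness, session length and number of sessions.
- **1b, retention:** "We will achieve follow-up rates of at least 80% at the 3-month follow-up".
- **1c, data completeness:** "Rates of missing/unusable data will be < 10% of all data collected".

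For each one the stated analysis is descriptive statistics only. Section 1.6 B lists the ratings among the primary outcomes without repeating the bar. Neither section gives a denominator, a form, a timepoint or a rule for a missing rating.

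Sections 1.5 and 6.1 B allow for "up to 20% loss to follow-up (i.e., 80% retention rate") and state the recruitment goal: "We will therefore aim to recruit 34 additional participants to have" 27 with complete follow-up data. The one imputation rule is "While we will impute baseline data where follow-up data are missing (i.e., assuming no improvement").

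Section 1.4 says of the pilot that "we could successfully follow-up this population (20 of 26 participants were reached at end-of-treatment"), and that "57.7% of participants met our target of attending at least 6 of 8 sessions". It also gives the pilot's acceptability results as percentages of participants. In section 1.9 B, both the Weekly Exit Interview and the Final Exit Interview are described as collecting usefulness ratings, and a Patient Satisfaction Survey is listed as well.

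**The concern.** Taken word for word, someone who gives no rating has not provided a 5 or more, so a lost participant would count against acceptability. The imputation rule cannot help, because a rating of treatment has no baseline value. Criterion 1c pools all data, so it does not say how one missing rating counts.

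On that reading, the retention figures in the document leave no room. If ratings come only from a visit attended by about 80% of participants, a treatment that every rater liked could still be reported as missing its bar. Criterion 1a would then largely re-measure retention, which 1b already covers. If the analyst divides by raters instead, the bar can be met while under two-thirds of those enrolled are known to be favourable. The same data could therefore be called a pass or a fail on a listed primary outcome.

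**Working it through.** **Inputs.** The bar is 80% (6.1 A). The sample size uses dz = 0.5, one-tailed alpha 0.05, 80% power and 20% loss (1.5, 6.1). The pilot counts and percentages are in 1.4.

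**The plan's own figures.** A one-sided paired t-test with these inputs needs n = 26.14, rounded up to 27. Allowing for loss, 27/0.80 = 33.75, rounded up to 34. Both stated numbers reproduce.

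**Non-raters counted as failures.** The number required is 0.80 × 34 = 27.2, so 28, and 28/34 = 82.4%.

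- 27 raters: at most 27/34 = 79.4%, one person short.
- Pilot end-of-treatment rate: at most 20/26 = 76.9%.
- 28 raters: 1b would be met at 82.4% if the same 28 are followed up, but all 28 must be favourable.
- 30 raters: 28/30 = 93.3% must be favourable.
- 32 raters: 28/32 = 87.5%.

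In general the share of raters who must be favourable is 0.80 divided by the rating rate, apart from rounding. With 61 participants (4.1, 4.5 C), 0.80 × 61 = 48.8, so 49 are needed and 12 non-raters can be absorbed.

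**Raters only.** With 27 raters, 0.80 × 27 = 21.6, so 22 pass (22/27 = 81.5%). Over all 34 that is 22/34 = 64.7%. With 27 raters, every count from 22 to 27 favourable passes on raters and fails on enrolled.

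**Chance of meeting the bar on one item.** Assume each of 34 participants rates with probability r, each rater is favourable with probability 0.90, and the two are independent. None of these values is in the plan. Over all enrolled, the chance is P[Bin(34, 0.90r) ≥ 28]. Among raters, it is the sum over m of P[Bin(34, r) = m] × P[Bin(m, 0.90) ≥ 0.80m].

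| Rating rate r | All enrolled | Raters only |
|---|---|---|
| 80% | 12.2% | 95.1% |
| 85% | 28.2% | 95.6% |
| 90% | 52.5% | 96.1% |
| 95% | 78.5% | 96.1% |
| 100% | 95.2% | 95.2% |

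The denominator matters unless nearly everyone rates. The question is whether the document adopts the strict one.

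**Which denominator the document has used for ratings.** The pilot percentages are 68.8, 18.8, 56.3 and 25. Among denominators from 1 to 26, only 16 reproduces all four: 11/16 = 68.75%, 3/16 = 18.75%, 9/16 = 56.25%, 4/16 = 25%. The combined 81.3% for helpfulness is 13/16; over all 26 it would be 13/26 = 50.0%. So percentages of participants for this kind of item were taken over raters (inferred from the percentages, not stated).

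**Whether the retention figures apply to ratings.** The 27 of 34 is what remains after the largest loss the plan allows for. It falls below 80% only because 33.75 was rounded up (27/33.75 is exactly 80%). The 20 of 26 comes from the earlier pilot, where section 1.4 reports sessions missed through transport problems; section 1.3 A gives travel difficulty as a reason for remote delivery. Both figures describe assessment visits. A participant who leaves before week 8 may already have rated usefulness on a weekly form.

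**The case for a change.** The strongest reply is that section 1.4 uses the same phrase, percent of participants, for attendance, where 57.7% is 15/26, all enrolled. One phrase with two denominators in one section means past practice does not settle the matter. The stakes are also visible there: 81.3% helpful among raters against 50.0% over everyone. Leaving form, timepoint and denominator open lets them be chosen after the data are seen, and fixing them would cost only wording.

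Part of this stands. The denominator is not stated, and neither is the form, the timepoint, or whether each of the three items must reach 80%. But attendance is known for every participant, so it has no non-raters and says little about how a missing rating is handled. The acceptability items are the closer precedent, and they point to raters.

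Nor does writing down a choice resolve the substance. A bar on raters leaves the views of those lost unseen. A bar on all enrolled mixes in retention, which 1b reports separately. Neither denominator is clearly better. Presenting the number rated, the number favourable and the number enrolled lets a reader compute either rate, and that is ordinary practice for a descriptive result.

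**Conclusion.** The claim that the 80% bar cannot be reached does not hold as a statement about the plan. It needs two conditions the document does not set: that non-raters count as failures, and that ratings come only from a visit with about 80% retention or less. If both held, 28 of 34 would be needed and 27 raters would fall one short. On raters only, 22 of 27 passes.

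The remaining gap is missing detail. It is confined to a descriptive benchmark in a single-group feasibility study: no test is attached to 1a, and no stated decision depends on it. An analyst would sensibly report the rate among raters, as the pilot appears to have done, with the number rated and the number enrolled beside it; criterion 1b shows retention separately. The choice of denominator is a fair trade-off, so no change follows.

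This rests on the inference that the pilot ratings had 16 respondents, and on reading the weekly form as a possible source of ratings, which the plan describes but does not tie to 1a. The pass probabilities are illustrations under an assumed 90% favourable rate and independence, not forecasts.
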